#### **6.4.5. AUDIT-C/AUDIT**

The AUDIT-C and, if the participant screens positive, the full AUDIT, will be repeated at weeks 4 and 8 in support of secondary objective 3.

#### **6.4.6. K6**

The K6 will be repeated at weeks 4, 6, and 8 in support of secondary objective 3.

#### **6.4.7. PHQ-9**

The PHQ-9 will be repeated at weeks 4 and 8 in support of secondary objective 3.

#### **6.4.8. GAD-7**

The GAD-7 will be repeated at weeks 4 and 8 in support of secondary objective 3.

#### **6.4.9. SF-12**

The SF-12 will be repeated at weeks 4 and 8 in support of secondary objective 4.

#### **6.4.10. Short Pain Scale**

The short pain scale will be repeated at weeks 4 and 8 in support of secondary objective 3.

#### **6.4.11. Current Medications**

Current medications will be reassessed at weeks 4 and 8 in support of secondary objective 2.

#### **6.4.12. Additional Questions**

Additional questions will be asked of study participants at follow-up time points as follows.

*Subjective Assessment of Change.* For purposes of stratifying participants for qualitative analysis (see [Section 3.2](#)), we will ask participants overall how they are feeling at 2, 4, 6, and 8 weeks post initial treatment compared to how they were feeling before having the procedure. Response options will be categorical.

*Subjective Assessment of Treatment Group.* At week 4, in order to analyze participants' beliefs regarding whether they were randomized to the study's active or sham treatment arm (in support of secondary objective 2), we will ask participants whether they believe they received an "active" procedure or an "imitation" procedure.

#### 6.4.13. Managing Distressed Participants during Automated Assessments

Ensuring the well-being of study participants is of paramount importance, particularly when utilizing web-based self-assessments to monitor PTSD symptoms and suicidal ideation. Our web-based system will have the capability to send messages to the participant and to key study staff in the event that a participant indicates a clinically significant risk of suicide. If an individual answers “yes” to any of the initial seven questions concerning suicidal ideation in the past two months, they then will be asked an additional 4 questions regarding *current* suicidal ideation or plans. If a participant answers affirmatively to currently wanting to harm themselves, thinking about committing suicide, have a plan, or are planning to act on a plan, an automated system will be triggered with the following results:

- A message will be displayed on the participant’s screen that says the following:  
“Given your responses to some of these questions, we are concerned about your safety. As you were told when you signed your consent form to participate in this study, we are contacting your Command in an effort to make sure that you are safe. We would like for you to please go to your nearest Emergency Room for assistance. In addition, please click below to indicate that you agree not to harm yourself before you get to the Emergency Room.”
- A text message providing the service member’s name and his/her command contact information (name, telephone number, and email) will be generated and sent to the following RTI staff:
  - The RC at the site
  - [name] ([name])
  - [name] ([name])
- RTI staff will contact the participant’s command by first calling the CQ/duty phone number. If that is unsuccessful, they will contact the participant’s First Sergeant or Commanding Officer.
  - The RC will be the first level responder, since he/she is local
  - If the RC doesn’t respond in 2 hours, [name] and [name] will respond.
- Per site policy, Behavioral Health will be notified by the following business day.

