#### 6.2.3.4. *Mini-International Neuropsychiatric Interview (M.I.N.I.)-Plus Suicidality Items (Appendix 7)*

The M.I.N.I.-Plus is a structured interview for diagnosing DSM-IV and ICD-10 psychiatric disorders (Sheehan et al., 1998). This study will use a subset of items from the full instrument geared toward identifying individuals experiencing suicidal ideation in the past 2 months. Response options are dichotomous (yes/no) and questions ask about desire, thoughts, planning, taking steps toward, and attempting suicide as well as deliberate injury without intent to kill oneself. Individuals answering affirmatively to any of the first 7 items regarding suicidal ideation in the previous 2 months will be asked to complete an additional 4 questions regarding any *current* desire to harm themselves, thoughts about suicide, plans for suicide, and active steps they may be taking.

The suicidal ideation assessment will be administered at initial screening so as to identify (and exclude) individuals deemed to be at elevated risk for suicide attempt. Those who screen positive on the M.I.N.I.-Plus items, who are then asked the follow-up items regarding current ideation, will be excluded from the study; they will be evaluated and managed per the appropriate site-specific Standard Operating Procedure (SOP). The assessment will also be administered on weeks 0, 2, 4, 6, and 8. Because screening will already have taken place, these enrolled participants will still be included in the study. This instrument will enhance participant safety and support secondary objective 3.

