#### **6.4.4. M.I.N.I.-Plus Suicidality Items**

The M.I.N.I.-Plus Suicidality Items will be repeated at weeks 4, 6, and 8, and is intended to enhance participant safety and support secondary objective 3. In most cases these assessments will take place via a secure web portal on the participant's device of choice (i.e., there will be no interaction between the participant and the RC at these times). If an individual affirmatively on any of the first seven M.I.N.I.-Plus items regarding suicidal ideation in the previous 2 months, they will be asked an additional 4 questions regarding *current* suicidal ideation or plans. If a participant answers affirmatively to currently wanting to harm themselves, thinking about committing suicide, having a plan, or planning to act on a plan, an automated participant safety system will be triggered (see [Section 6.4.13](#)).

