### 7.2. Adverse Events

An adverse event (AE) is any untoward medical occurrence in a clinical investigation participant administered a medicinal product and which does not necessarily have a causal relationship with this treatment. An AE can therefore be any unfavorable and unintended sign, symptom, or disease temporally associated with the use of a medicinal product, whether or not considered related to the medicinal product. AEs may also include pre- or post-treatment complications that occur as a result of protocol-mandated procedures (e.g. invasive procedures such as venipuncture, biopsy, etc.). Pre-existing events which increase in severity or change in nature during or as a consequence of use of a medicinal product in human clinical trials will also be considered AEs.

Any reported medical condition or clinically significant laboratory abnormality with an onset date before the screening visit and not related to study procedures is considered to be pre-existing, and should be documented in the case report form.

Any AE (i.e., a new event or an exacerbation of a pre-existing condition) with an onset date after the screening visit up to the last day on study (including the follow-up, off study medication period of the study), should be recorded as an AE on the appropriate CRF page(s).

An AE does not include:

- Medical or surgical procedures (e.g. surgery, endoscopy, tooth extraction, transfusion); the condition that leads to the procedure is an adverse event.
- Pre-existing diseases or conditions or laboratory abnormalities present or detected prior to the screening visit that do not worsen.
- Situations where an untoward medical occurrence has not occurred (e.g. hospitalization for elective surgery, social and/or convenience admissions).
- Overdose of either study drug or concomitant medication without any signs or symptoms unless the participant is hospitalized for observation.

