## **7.6. Serious Adverse Event Reporting Requirements**

### **7.6.1. All Serious Adverse Events**

RTI International, the Research Monitor, and HRPO must be notified immediately regarding the occurrence of any unanticipated and/or serious adverse event that occurs after the screening visit, including serious adverse events resulting from study procedures performed from screening onwards. The procedures for reporting all serious adverse events, regardless of causal relationship, are as follows:

- Record the unanticipated and/or SAE on the AE CRF and complete the “Serious Adverse Event Report” form.
  - Fax and email the serious adverse event report to the attention of RTI International and HRPO within 24 hours of the investigator’s knowledge of the event. Contact information is below.
  - For fatal or life-threatening events, also fax and email copies of hospital case reports, autopsy reports, and other documents when requested and applicable.

RTI International Principal Investigator: Name: [name] [name]  
Title Chief Medical Officer  
[contact]  
Mobile [contact]  
Email: [[contact]](mailto:[contact])

RTI International Co-Investigator: Name: [name]  
[contact]  
Mobile [contact]  
[contact]  
Email: [[contact]](mailto:[contact])

HRPO: [contact]  
[contact]  
Email: [[contact]](mailto:[contact])

Research Monitor: Name: MAJ [name] MD  
[contact]  
[contact]  
[contact]  
Email : [[contact]](mailto:[contact])

RTI International may request additional information from the Investigator to ensure the timely completion of accurate safety reports.

The Investigator must take all therapeutic measures necessary for resolution of the SAE. Any medications necessary for treatment of the SAE must be recorded onto the concomitant medication section of the participant's CRF.

Follow-up of adverse events will continue through the last day on study (including the follow-up, off study medication period of the study), until the Investigator and/or RTI International determine that the participant's condition is stable, or up to 30 days after the last dose of study drug, whichever is longer. RTI International may request that certain adverse events be followed until resolution.

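### After enrolment, a reported past-2-month suicide attempt, preparatory step or self-injury with no current ideation starts none of the responses in protocol section 6.4.13, and no supplied text routes the answer to anyone for clinical contact or AE/SAE assessment

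*Protocol*

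**What the plan says.** Protocol section 6.2.3.4 describes seven M.I.N.I.-Plus items with a 2-month look-back. Beyond desire, thoughts and planning, they cover "taking steps toward, and attempting suicide as well as deliberate injury without intent to kill oneself". The items are given at screening and at weeks 0, 2, 4, 6 and 8, and sections 6.2.3.4 and 6.4.4 both give participant safety as one purpose.

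At screening, a positive answer excludes the person, who is then evaluated and managed under the site's SOP. For later administrations, section 6.2.3.4 says: "Because screening will already have taken place, these enrolled participants will still be included in the study".

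Sections 6.4.4 and 6.4.13 set the post-enrolment rule. Any yes among the seven items opens four questions about the present, and the automated system starts when the participant "answers affirmatively to currently wanting to harm themselves, thinking about committing suicide, have a plan, or are planning to act on a plan". The last listed result is: "Per site policy, Behavioral Health will be notified by the following business day". At weeks 4, 6 and 8 the items are in most cases completed on the participant's own device, and "there will be no interaction between the participant and the RC at these times".

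**The concern.** The items ask about acts as well as thoughts, but the trigger looks only at present ideation or plans. Someone who harmed themselves three weeks ago and feels no such urge today can truthfully answer yes to a past item and no to all four current ones. Consent may add to this pattern: section 9.1.3.1 tells participants that indicating an intention to harm themselves leads to command notification, and section 1.1.2 describes stigma as a deterrent to care. That some would disclose a past act and deny present intent is an inference, not something the documents report.

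Two things are at stake. A participant who has had an experimental injection and then reports an attempt may not be contacted because of that report. The event may also stay out of the AE/SAE record until someone learns of it another way. The items repeat under the same rule, so the same answer pattern again starts nothing, and after week 8 there is no further automated screen.

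**Working it through.** No formula applies. The check follows one answer pattern through the text and then asks whether another provision picks it up.

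**Path of the answer (protocol 6.2.3.4, 6.4.4, 6.4.13)**

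1. Past-2-month attempt, preparatory step or self-injury: yes.
2. Four current items are asked: all no.
3. Trigger condition (at least one current yes): not met.
4. Responses listed as results of the trigger: screen message, text to staff, command contact, Behavioral Health notice. That is 4, and 4 of 4 need step 3 to be met.
5. Stated consequence of a post-enrolment positive without a current yes: the participant remains in the study. No contact, notice or assessment is stated.

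**Setting.** From week 0 there are 5 administrations (weeks 0, 2, 4, 6, 8). Three of them (weeks 4, 6, 8) normally involve no contact with the Research Coordinator (RC).

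**Other provisions that might catch it**

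- *Clinic visits, weeks 0 and 2 (protocol 3.1, 6.3).* Nursing staff take an interim history and review of systems, and the physician takes a targeted history. This could bring out the event. Review of the M.I.N.I.-Plus answers is not stated.
- *Week 8 CAPS-5 call (6.2.2.4, 6.4.1).* Trained interviewers use a distress protocol covering passive and active suicidal thoughts. It acts on what is said in the call, and nothing links it to the stored answers.
- *AE rules (7.2, 7.3).* A new attempt or self-injury after screening would be an AE and should be recorded. No text sends the questionnaire answer into AE review.
- *SAE rules (7.6.1).* If the event is serious, the report is due "within 24 hours of the investigator’s knowledge of the event". Nothing in the path above gives the investigator that knowledge.
- *RC oversight, CRF signature and monitoring (6.1, 9.1.5, 9.3.1).* The RC oversees assessments, a site investigator signs CRFs within a reasonable time, and the monitor reviews them at regular intervals. The text does not say that the web questionnaires are CRFs or that these answers are read on receipt.
- *On-call clinician (SAP 2.3.3).* The SAP assigns the four current items to an on-call behavioral health clinician, without limiting this to yes answers. It gives no timing or action and points to a later discussion that does not appear. It also opens the four items at a score of 9 or more, whereas the protocol opens them at any yes. It gives 9 points to active preparatory steps but states no value for an attempt or for self-injury.

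Each provision could bring the event to light; none is started by the answer itself.

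**The case against.** The strongest reply is that section 6.4.13 is a deliberate two-stage screen: past positive, then a probe of present risk, then an emergency response. Reserving command contact for present risk is sound triage, and that stands.

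It can also be said that the sentence keeping enrolled participants in the study concerns eligibility only and does not switch off SOP evaluation. That is fair. A reader might infer that the protocol withdraws SOP management after enrolment, but it does not say so; it simply states SOP evaluation only for screening positives.

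The on-call clinician in the SAP is relevant contrary evidence. For preparatory steps, which alone reach the SAP's threshold, the documents name a clinical user of the follow-up answers even when all four are no. Without a stated time, action or route, this softens the gap but does not close it.

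The AE/SAE rules already impose the reporting duty, so part of any remedy repeats them. What is missing is the step by which the answer reaches someone who has that duty.

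Finally, Appendix 7 (the items), Appendix 10 (the distress protocol) and the site SOPs were not available. Any of them may contain the missing instruction.

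**Conclusion.** The gap holds for the supplied protocol text. Following 6.4.4 and 6.4.13 exactly, a yes to an attempt, preparatory-step or self-injury item with four current no answers triggers none of the four listed responses. No supplied provision routes the stored answer for contact or AE/SAE assessment.

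A reader might infer that such a report would certainly go unnoticed, or that the trial has no suicide safeguards. The documents support neither. Present ideation has a defined response, and the clinic histories, CAPS-5 call, AE/SAE rules and SAP clinician may each catch the event. Nor can it be said that no rule exists anywhere, given the unseen appendices and SOPs.

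The number affected is unknown and probably small. Section 4.1.3 excludes suicidal ideation in the 2 months before screening, and the case then needs a new act, its disclosure and four current no answers. The documents give no rate and none is assumed. This is an inexpensive improvement, justified by the gravity of the event rather than its frequency. Confidence is moderate because of the unseen material.

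**What to change.** If an appendix or site SOP already covers this answer pattern, add a cross-reference in 6.4.13. Otherwise amend 6.4.4 and 6.4.13 as follows.

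1. A yes to the attempt, preparatory-step or self-injury item sends a staff-only notice even when all four current items are no. It has its own text and does not start command contact, which stays tied to the current items and the consent wording.
2. The notice goes to the RC and a blinded clinician, such as the on-call behavioral health clinician or a blinded co-investigator. It does not go to the injecting physician except as safety requires: section 5.3 has the site investigator give the injection, section 5.1 leaves injecting physicians unblinded, and suicidality is a secondary outcome.
3. That clinician contacts the participant as clinically indicated under the site SOP.
4. A blinded assessor judges the event as an AE/SAE, and it is reported under 7.6 if serious. An event already assessed is flagged so that repeat notices can be closed.

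The cost is IRB approval before implementation (section 9.1.2), one alert condition with separate text, and one AE instruction. The look-back means one event can recur in the answers. At nominal dates, an event one day before week 0 lies 56 + 1 = 57 days before week 8, inside a look-back of about 60 days. It could therefore produce at most 5 notices (weeks 0, 2, 4, 6, 8). An event after week 0 could produce at most 4.

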#### 6.2.2.4. Managing Distressed Respondents During CAPS-5 Administration

A number of measures will be taken to enhance the safety of potentially distressed participants during telephone CAPS-5 administration. First, we will provide explicit protocols for CIs to follow if they encounter either passive or active suicidal or homicidal thoughts. Training and supervision will be provided for managing respondents who express sadness, agitation, frustration, or any other strong emotion during the course of the clinical interview. A detailed Distressed Respondent Protocol (DRP) (**Appendix 10**), which has been successfully used for the NSDUH Mental Health Surveillance Study, will be employed for this study. The DRP provides definitions and examples of five types of distressed respondents, along the continuum of no risk of harm (i.e., respondent is agitated or upset) to imminent danger (e.g., respondent reports active suicidal thoughts, a plan, and a means to carry out that plan). The DRP then gives step-by-step instructions for handling each of the five types of distressed respondents. CIs will be thoroughly trained in the use of the DRP.

The DRP will be very similar to the system described in [Section 6.4.13](#) regarding management of distressed participants during automated assessments. Clinical interviewers will inform individuals at the beginning of the CAPS-5 that they need to obtain the individual's physical location (address) for the purposes of safety, that such information will not be stored, and that it will only be used in the case of an emergency. In the event that a respondent indicates *active* suicidal or homicidal ideation during their CAPS-5, the clinician administering the

CAPS-5 will call or (in the event that keeping the respondent on the phone is advisable) send a text message to study co-investigator [name] and study logistics director [name] indicating the nature of the ideation, physical location of the respondent (if known), and contact information for the respondent. [name] or [name] will immediately call the respondent's CQ/duty phone number, CO, or 1SG to report the incident. Given the emergent nature of *active* suicidal or homicidal ideation, we believe that using text messaging and/or telephone communications is justified.

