#### 9.1.3. After local IRB approval, the Protocol then must be submitted to HRPO for approval, which also must be documented before enrolling of participants may begin. ’ Informed Consent

##### 9.1.3.1. Effectiveness Clinical Trial

For the effectiveness clinical trial, it is the responsibility of the Investigator or his designee (e.g., the Research Coordinator) to obtain written informed consent from each individual participating in this study after adequate explanation of the aims, methods, objectives, and potential hazards of the study and prior to undertaking any study-related procedures. The discussion must take place in a private setting. The Investigator must utilize an IRB-approved consent form for documenting written informed consent. A model consent form is provided in **Appendix 20-1**. Each informed consent will be appropriately signed and dated by the participant and the person obtaining consent; all other pages of the consent are to be initialed by the participant, also. The informed consent form does not explicitly describe the Horner’s syndrome evaluations to be performed by the RC; they add no risk, and we do not wish to draw attention to this participant-observable phenomenon which may unblind the participant.

During the consent process it will be made clear to potential participants that if they indicate an intention to harm themselves or somebody else during the trial, their command will be notified. This includes verbal indications as well as those during online assessments, should relevant items be answered in such a way as to indicate emergent suicidal ideation. Those indicating emergent suicidal ideation during an online assessment (Section 6.4.13) will see a message on their screen recommending that they go to their nearest Emergency Department

(ED) for assistance. These individuals will also be asked to confirm (via checking a box on the screen) that they will not act on any suicidal thoughts before presenting to the ED.

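### After an online report of current self-harm intent, suicidal thoughts or a plan, Protocol 6.4.13 sets no time for the coordinator's call to command and obliges the back-up staff to act only after 2 hours

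*Protocol*

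**What the plan says.** **Online pathway (Protocol 6.4.13).** A yes to any one of four current items (wanting to harm oneself, thinking about suicide, having a plan, planning to act on it) triggers an automated response. The participant sees a message directing them to an Emergency Room and is asked to agree not to harm themselves before getting there. The site Research Coordinator (RC) and two other staff receive a text with the participant's name and command contact details. Staff are to telephone the duty number and, if that fails, the First Sergeant or Commanding Officer. No time is given for this call. On the order of response the section says "The RC will be the first level responder, since he/she is local", and the other two respond "If the RC doesn’t respond in 2 hours". The only other notification time is "Per site policy, Behavioral Health will be notified by the following business day".

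**Telephone pathway (Protocol 6.2.2.4).** When an interviewer hears active suicidal or homicidal ideation during the CAPS-5, the interviewer calls or texts two study staff, one of whom "will immediately call the respondent"'s duty phone or commanders. The section introduces its procedure with "The DRP will be very similar to the system described in" Section 6.4.13.

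**Setting.** Protocol 6.4.4 says of the suicidality items at weeks 4, 6 and 8 that in most cases "there will be no interaction between the participant and the RC at these times".

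**The concern.** A participant who discloses online is usually alone with a screen. By telephone, a clinician is on the line and has asked for the participant's physical location. Online, the call to command is the only prompt human contact that Section 6.4.13 itself requires of staff, since Behavioral Health may be told as late as the next business day.

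That call has no deadline for the person named to make it first. The two colleagues who already hold the same contact details have no duty to use them until the RC has been silent for 2 hours. The rule makes no distinction by severity, so it applies equally to someone who reports planning to act on a plan. An RC could plausibly miss a text: Protocol 3.1 pays for assessments completed in off-duty hours, so some alerts may arrive outside working time. That last step is an inference, because the documents give no rate of RC non-response.

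What is at stake is avoidable delay in a safety response, in a situation where the possible harm is death.

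**Working it through.** The 2 hours is a procedural rule. It is not derived from other inputs, so there is no figure to reproduce. The check is a comparison of the two sections.

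| Feature | Online (Protocol 6.4.13) | Telephone (Protocol 6.2.2.4) |
|---|---|---|
| Trigger | Self-reported yes to any one of four current items | Active suicidal or homicidal ideation heard by a clinician |
| Who is alerted | RC and two other staff, by automated text | Two study staff, called or texted by the interviewer |
| Time for the alerted staff to call command | None stated for the RC; none for the other two until 2 hours of RC non-response | Immediately |
| Back-up clock if the alert is missed | 2 hours | None |
| Human contact at the moment of disclosure | Usually none | Interviewer on the line |
| Immediate automatic safeguard | Emergency Room message and agreement not to self-harm | Not applicable |

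**Step 1: what the 2 hours governs.** The sentence sits under the bullet on contacting command, so the natural reading is that responding means making that contact. The protocol does not define the word or say when the clock starts. If responding meant only acknowledging the text, the gap would be wider, because an acknowledgement would stop the clock with no call made.

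**Step 2: whether another section supplies a deadline.** Protocol 6.2.3.4, 6.4.4 and 9.1.3.1 and SAP 2.3.3 give none for contacting command after an online disclosure. Protocol 9.1.3.1 says "Those indicating emergent suicidal ideation during an online assessment (Section 6.4.13) will see a message on their screen", and says that command will be notified, without a time. SAP 2.3.3 mentions an on-call behavioral health clinician who uses the four current items, but it gives no alert route or time and uses a different trigger (a score of 9 or more). Section 6.4.13 texts no such clinician.

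**Step 3: how many occasions the rule covers.** Inputs: 240 participants (Protocol 6.1), three online time points (weeks 4, 6 and 8, Protocol 6.4.4), and the 25% attrition considered in Protocol 8.4.

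- No attrition: 240 × 3 = 720 planned administrations.
- All attrition before week 4: 240 × (1 − 0.25) = 180, and 180 × 3 = 540.

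The range of 540 to 720 counts questionnaires on which an unattended disclosure could occur. The number actually unattended may be lower, because Protocol 6.4.4 says this holds in most cases. No number of disclosures can be computed, because the documents give no rate. Protocol 4.1.3 excludes suicidal ideation in the past 2 months, which points to a small number.

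**The case against.** The case for leaving the text alone has real content.

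- **The two times are different kinds of rule.** The immediate call by telephone is a duty on staff who have been alerted. The 2 hours online is a back-up for an RC who does not answer. The telephone pathway has no back-up clock at all, so on that point the online pathway is the better specified. This stands, and it rules out reading the contrast as 2 hours against zero for the same event.
- **The online trigger is broader.** A single self-reported yes, including to thinking about suicide, is not the same as active ideation judged by a clinician. A tiered, local-first response to a broader trigger is defensible. This stands in part: the 2 hours also covers a yes to planning to act, where the difference in trigger does little to justify waiting.
- **Shared wording proves little.** A reader might infer that the protocol itself sets the same urgency for both pathways, because 6.2.2.4 says "Given the emergent nature of" active ideation and 9.1.3.1 uses the same adjective for online disclosures. The documents do not support that. In 6.2.2.4 the phrase justifies using text messages and telephone, which concerns the channel and not a deadline. In 9.1.3.1 it introduces the on-screen message.
- **Help is not withheld for 2 hours.** A reader might also infer that nothing happens in that time, or that the back-ups are told to wait. Neither is so. The Emergency Room message and all three texts are automatic, and nothing stops any recipient from calling sooner. What remains is that nothing requires it.
- **Unseen documents.** The Distressed Respondent Protocol (Appendix 10) and the site procedures are not in the supplied text and might contain a time. Section 6.4.13 cites none from them for the call to command.

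**Conclusion.** The point holds as a modest safety tightening. Section 6.4.13 leaves the RC's call to command without a time, and it gives the two other recipients no duty to act before 2 hours of RC non-response, whatever the severity of the disclosure. Staff alerted by telephone to active ideation must call at once. The documents do not show that online disclosures go unanswered, that the 2 hours is a prescribed wait, or that the two pathways were meant to share a deadline.

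Few participants are likely to be affected. The 540 to 720 planned administrations bound the opportunities and say nothing about how often a disclosure or a missed text would occur. The change is still worth making because the possible harm is grave and all three recipients already hold the information needed to act. The conclusion assumes that responding means contacting command, and that no time limit for that call stands in Appendix 10 or the site procedures.

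**What to change.** Keep the RC as first responder and replace the two sub-bullets on order of response in Protocol 6.4.13 with:

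> The RC will call command immediately on seeing the alert and will confirm the completed call to the other two recipients. Either of the other two who sees the alert will at once try to reach the RC and, if the RC cannot be reached or has not called, will call command immediately and tell the others. In any case, if no completed call has been confirmed within 2 hours of the alert (or a shorter limit set with the IRB), both will call command.

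This gives the RC's call a time, starts the back-ups' duty when they see the alert, and defines both ends of the outer limit (from the alert to a confirmed call). Checking with the RC first preserves the local-first tier and limits duplicate calls to a service member's command, which matters given the stigma concerns in Protocol 1.1.2.

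The cost is two sub-bullets, with no new staff and no system change, because all three already receive the text. The duty to call at once begins on seeing the alert, so it adds no round-the-clock cover. The downside is an occasional duplicate call. An alert that nobody sees is still not covered, a limit the telephone pathway shares.
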